## 9.4 Follow-up visits

The following procedures are performed at all scheduled follow-up visits:

- Risk reduction counseling (as described in Section 9.7);
- Pregnancy prevention assessment (as described in Section 9.2 and 9.8); and
- Assessment of new or unresolved social impacts (site staff will ask participant about the status of any unresolved social impacts and if s/he has experienced any new social impacts as a result of the trial participation);

- Assessment of new or continuing concomitant medications (as described in Section 9.2); and
- Assessment of new or unresolved AEs/intercurrent illnesses.

Additional procedures will be performed at scheduled follow-up visits as specified in Appendix K and Appendix L:

- Administration of the social impact assessment questionnaire (types of impacts assessed involve personal relationships, health insurance, life insurance, educational or employment opportunities, housing, immigration, or travel);
- Administration of a questionnaire that asks the participant about any HIV testing he or she may have received outside of the study. Participants will also be asked whether they believe they received the active vaccine or the control;
- HIV infection assessment including pre-test counseling. A subsequent follow-up contact is conducted to provide post-test counseling and to report results to participant;
- Confirm that participants received HIV test results from previous visit. If not, provide test results and post-test counseling as appropriate;
- Abbreviated physical examination including weight, vital signs, and a symptom-directed evaluation by history and/or appropriate physical exam based on participant self-reported symptoms or complaints;
- Complete physical examination, including weight, vital signs, and clinical assessments of head, ears, eyes, nose, and throat; neck; lymph nodes; heart; chest; abdomen; extremities; neurological function; and skin;
- Specimen collection;
- **In Part B**, specimen collection includes optional stool sample (see Appendix L). Collect dietary, antibiotic use, and gastrointestinal symptom information from participants providing stool specimen.
- Clinical laboratory tests including:
  - CBC with differential,
  - Chemistry panel (see Section 9.2), and
  - Urine dipstick (urinalysis if appropriate; see Section 9.9); and
- Urine or serum pregnancy test (for participants who were born female). Persons who are NOT of reproductive potential due to having undergone total hysterectomy or bilateral oophorectomy (verified by medical records), are not required to undergo pregnancy testing.

## 9.5 Contact at 6 months after last scheduled visit

CRS staff will contact study participants at 6 months after the last scheduled visit to collect the information listed below. This contact may be accomplished by phone, text message, or email. If indicated, the participant may be asked to come in for a clinical assessment which may also include referrals for AESI assessment. AESIs are described further in Appendix M.

- Confirmation of vital status; if deceased, attempt to learn cause and date of death
- If participant is alive, record the participant's responses to the following:
  - Assessment of new or unresolved AEs/intercurrent illnesses:
    - Life threatening adverse experiences;
    - Persistent or significant disability/incapacity;
    - Hospitalizations and reasons;
    - Other important medical events that may jeopardize the participant or may require intervention to prevent 1 of the other outcomes listed above;
    - New chronic conditions requiring more than 30 days of medical intervention or medication;
    - AESI (Section 11.2.2. A sample list of AESI is provided in Appendix M);
    - New diagnosis of HIV infection; and
    - Pregnancies and outcomes, including congenital anomalies/birth defects.

All such events will be recorded and adverse events will be assessed for relationship to study products.

### 9.5.1 Interim contacts

CRSs may report safety information obtained at a contact other than scheduled contacts. These contacts are reported as interim visits.

## 9.6 Stool sample collection in Part B

Three stool samples will be collected from the study participants in Part B who agree to this procedure: 1 prior to enrollment (before the injection of the vaccine), 1 at the Month 8.5 timepoint, and 1 at the Month 16.5 timepoint. These samples will be collected using swabs, either via rectal swabs or by taking swabs from stool. If bulk stool is provided, a portion may be kept for further analysis.

## 9.7 HIV counseling and testing

HIV counseling will be performed in compliance with the CDC's guidelines or other local guidelines for HIV counseling and referral. HIV testing will be performed in accordance with the current HVTN HIV testing algorithm following enrollment.

Participants will be counseled routinely during the trial on the avoidance of HIV infection and on the potential negative social impacts of testing antibody positive due to the vaccine. They will also be counseled on the risks of HIV antibody testing outside of the HVTN CRSs and will be discouraged from doing so during study participation and/or during any period of vaccine-induced positive serology.

Study staff will take particular care to inform study participants of the likelihood of routine HIV testing being offered or performed outside the study CRS at emergency rooms, clinics, and medical offices. Such testing has become more likely due to the CDC's revised guidelines for HIV counseling and testing, as well as policy changes in many countries to make HIV testing more frequent and routine. CRS staff should inform participants of their right to opt out of HIV testing outside the study site. CRS staff should inform study participants if local and/or state policies and regulations permit medical providers to perform HIV testing without first informing patients. If this is the case, then CRS staff should advise study participants that they may decline testing preemptively. CRS staff should also inform participants if positive results must be reported to local public health authorities. CRS staff should also inform participants of the need to maintain study blinding by getting HIV testing only at the study CRS. CRS staff should provide participants with CRS contact information and should encourage participants to ask medical providers to contact the CRS. The CRS can verify that the participant is in an HIV vaccine clinical trial and should only be tested at the study CRS.

Potential participants identified as being HIV infected during screening are not enrolled. All participants who become HIV infected during the study will be terminated from this study. Potential and enrolled participants identified as HIV infected will be referred for medical treatment, counseling, and management of the HIV infection. These individuals may also be referred to appropriate ongoing clinical trials or observational studies.

### 9.7.1 Distinguishing intercurrent HIV infection from vaccine-induced positive serology

The study product may elicit an antibody response to HIV proteins. Therefore, vaccine-induced positive serology may occur in this study. Several precautionary measures will be taken to distinguish intercurrent HIV infection from vaccine-induced positive serology. These precautionary measures include:

- Participants will have physical examinations at visits specified in Appendix K and Appendix L. Signs or symptoms of an acute HIV infection syndrome, an intercurrent illness consistent with HIV-1 infection, or probable HIV exposure would prompt a diagnostic workup per the HVTN algorithm for Recent Exposure/Acute Infection Testing to determine HIV infection.
- HIV testing will be performed at multiple timepoints throughout the study (Appendix K and Appendix L). The Laboratory Program (or approved diagnostic laboratory) will follow the HVTN HIV testing algorithm (as described in the HVTN Laboratory Manual of Operations), which is able to distinguish vaccine-induced antibody responses from actual HIV infections.

- All participants can receive HIV-1 diagnostic testing from the site following their last scheduled visit until they are told that they did not receive an HIV vaccine or that they do not have vaccine-induced seropositivity.
- All participants who received vaccine product and who have vaccine-induced positive or indeterminate HIV-1 serology (as measured by the standard anti-HIV antibody screening tests) at or after the study is unblinded will be offered poststudy HIV-1 diagnostic testing (per the HVTN poststudy HIV-1 testing algorithm) periodically and free of charge as medically/socially indicated (approximately every 6 months) unless or until HIV Ab testing is no longer the standard test in clinical settings.

#### **9.7.2 VISP registry**

Experimental HIV vaccines may induce antibody production to HIV antigens, producing reactive results on commercially available HIV test kits. This is called “vaccine-induced seropositivity” (VISP) (see Section 9.7.1). In order to provide poststudy HIV testing to distinguish between VISP and HIV infection, and to mitigate potential social harms resulting from VISP in HIV vaccine recipients who are not infected with HIV, the HVTN has created a VISP registry. Following study unblinding, the registry will allow trained staff to verify that an individual has received an HIV vaccine, and therefore has the potential for VISP. Information in the VISP registry will not be used for research. Rather, the registry exists to support provision of poststudy testing and counseling services to HIV vaccine recipients. The registry contains the names of all study participants, unless they request that their names be removed.

#### **9.8 Contraception status**

Contraception status is assessed and documented at every scheduled clinic visit for a participant who was born female and who is sexually active in a way that could cause that participant to become pregnant. Prior to enrollment and throughout the study, staff will ask participants to verbally confirm their use of adequate contraceptive methods. A participant who was born female and is sexually active in a way that could cause that participant to become pregnant should be reminded at all scheduled clinic visits of the importance of using contraception and should be referred to specific counseling, information, and advice as needed. (Specific contraception requirements are listed in Section 7.1). This reminder should be documented in the participant’s study record.

Self-reported infertility—including having reached menopause (no menses for 1 year) or having undergone hysterectomy, bilateral oophorectomy, or tubal ligation—must be documented in the participant’s study record.

#### **9.9 Urinalysis**

Dipstick testing may be performed in the clinic or the lab, as long as the required elements (glucose, protein, and hemoglobin) are tested. The examination is performed on urine obtained by clean catch.

If the screening dipstick is transiently abnormal due to menses or infection, document this issue in the participant’s source documentation. For infection, provide appropriate

treatment and/or referral. Following resolution, repeat the dipstick and, if within the eligibility limits specified in the protocol, the participant may be enrolled.

Follow-up urinalysis should be deferred if a participant is menstruating, but should be performed as soon as possible. If a follow-up dipstick is abnormal due to a participant's menstrual period, document in the comment section of the case report form (CRF) and repeat the dipstick once the participant is no longer menstruating. A micro-urinalysis is not required.

## 9.10 Assessments of reactogenicity

For all participants, baseline assessments are performed before and reactogenicity assessments are performed after each vaccination. All reactogenicity symptoms are graded according to the Division of AIDS Table for Grading the Severity of Adult and Pediatric AdverseEvents, Version 2.0, November 2014, except as noted in Section 11.2.2.

The reactogenicity assessment period is 7 full days following each vaccination per the assessment schedule shown in Table 9-1. Participants are instructed to record symptoms using a postvaccination memory tool. Contact between the participant and the site staff should take place at least once within 72 hours/3 days postvaccination. Clinic staff will follow new or unresolved reactogenicity symptoms present at day 7 to resolution. Participants are instructed to contact the clinic for events that arise during the period between vaccination and the next scheduled visit. In general, a participant who self-reports any postvaccination reaction greater than mild is seen by a clinician within 48 hours after onset, unless the reaction is improving and/or has completely resolved.

Reactogenicity events are reported using CRFs that correspond to the time of assessment in Table 9-1. Reactogenicity assessments include assessments of systemic and local symptoms, vaccine-related lesions, and lymph nodes. Events not listed on a CRF, or with an onset after the reactogenicity assessment period (day of vaccination and 7 full days after), or those meeting SAE/adverse events requiring expedited reporting to DAIDS criteria, are recorded on an adverse experience log form.

**Table 9-1 Schedule of reactogenicity assessments**

Day	Time	Performed by
0 a	Baseline: before vaccination	HVTN CRS staff
	Early: 25-60 minutes after vaccination	HVTN CRS staff
	Between early assessment and 11:59pm day 0	HVTN CRS staff or participant
1	Between 12:00am and 11:59pm day 1	HVTN CRS staff or participant
2	Between 12:00am and 11:59pm day 2	HVTN CRS staff or participant
3	Between 12:00am and 11:59pm day 3	HVTN CRS staff or participant
4	Between 12:00am and 11:59pm day 4	HVTN CRS staff or participant
5	Between 12:00am and 11:59pm day 5	HVTN CRS staff or participant
6	Between 12:00am and 11:59pm day 6	HVTN CRS staff or participant
7 b	Between 12:00am and 11:59pm day 7	HVTN CRS staff or participant

a Day of vaccination

b New or unresolved reactogenicity symptoms present on day 7 are followed until resolution

#### **9.10.1 Assessment of systemic and local symptoms**

Systemic symptoms include increased body temperature, malaise and/or fatigue, myalgia, headache, chills, arthralgia, nausea, and vomiting. Local symptoms include pain and/or tenderness proximal to the injection site. The daily maximum severity reached for each symptom during the assessment period is reported.

Body temperature is measured by oral or infrared thermometry and reported in degrees Celsius. If temperature is measured in Fahrenheit, the conversion to Celsius should be documented in the participant's chart note. A measurement is taken once daily during the assessment period and should be repeated if participant is feeling feverish.

#### **9.10.2 Assessment of injection site**

Typical injection site reactions are erythema/redness and induration/swelling. The maximum horizontal and maximum vertical measurements for all injection site reactions are recorded.

All injection site reactions are monitored until resolution. Areas greater than 25 cm^2 are followed daily; otherwise, the frequency of follow-up is based on clinician judgment.

#### **9.10.3 Assessment of lymph nodes**

This assessment is required only when reactogenicity assessments are performed by HVTN CRS staff, not by the participant.

Only the proximally draining lymph nodes are assessed (eg, inguinal nodes on the same side of the body for injections given in the vastus lateralis). Lymph nodes are first evaluated for enlargement and tenderness. If they are found to be enlarged, measurements are taken to determine the size (widest diameter) of the enlarged node(s).

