compare the immunogenicity of the EnvSeq-1 vaccines with and without the DNA. The primary immunogenicity timepoints in Part B will occur after the fourth injection to permit sufficient time for the development of peak nAb titers and after the last vaccination to be able to evaluate whether the full regimens lead to the development of broadly neutralizing antibodies.

GLA-SE will be admixed with all proteins. The total dose of GLA-SE will be 10 mcg at all timepoints. The total volume for protein + adjuvant for injection is 1 mL, mixed 1:1 by volume.

If Part A indicates that the dose of each protein should be 20 mcg in Part B, the total dose of each protein in Groups 7 and 8 with the additive approach will also be 20 mcg. If the dose of each protein is determined to be 100 mcg or 400 mcg, the dose of each protein in Groups 7 and 8 will be 100 mcg to avoid going over 400 mcg of total protein at any timepoint.

All injections will be administered IM in the thigh. Part A injections will be administered as 1 mL of protein or placebo administered by needle and syringe. Part B injections will consist of 1 mL of protein or placebo administered by needle and syringe and 1 mL of DNA or placebo administered by needleless Biojector® into the same thigh. The rationale for injecting both products into the same limb is to ensure that both immunogens reach the same draining lymph nodes to optimize the amount of T-cell help available to promote B-cell differentiation and proliferation within the germinal center. Data from non-human primates (with different vaccine products) demonstrate that same limb co-immunization with DNA/gp120 protein/GLA-SE adjuvant vaccines resulted in enhanced humoral immune responses and polyfunctional cellular immune responses [28,34].

Adult immunizations are usually administered in 0.5 to 1 mL doses. There is, however, experience with the Hepatitis B vaccine Engerix-B, which has been safely given as a 2 mL injection in hemodialysis patients [29]. Similarly, multiple injections of licensed vaccines have been administered safely in the same limb, either the deltoid or the thigh [35,36]. As the 2 mL combined volume of the protein and DNA injections exceeds the typical volume administered in the deltoid, the larger vastus lateralis muscle will be used as the site of injection. To maintain comparability and blinding across groups, all groups will have all injections administered in the thigh.

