#### 4.9.3 Clinical studies of the DNA Mosaic-Tre *env* vaccine

The DNA Mosaic-Tre *env* vaccine, administered via Biojector, is currently being tested in HVTN 106 to evaluate the breadth of induced CD4 and CD8 T-cell responses compared to group M consensus Env CON-S and a wild-type transmitted/founder Env B.1059 with the same DNA backbone as the DNA Mosaic-Tre *env*. HVTN 106 enrolled 105 participants randomized to receive 3 injections of DNA Mosaic-Tre *env* (previously known as DNA Mosaic *env*), DNA CON-S *env*, DNA WT *env*, or placebo, with 30 participants in each active group and 15 participants in the control group. Participants randomized to active groups also received 2 doses of an MVA HIV vaccine boost. The final product administration was in May 2016. As of June 2016, study follow-up is ongoing and the study remains blinded. The vaccines have been well tolerated with the most frequent reactogenicity symptoms being local pain and/or tenderness at the injection site, with the majority being mild (see Table 4-6). There have been 6 AEs deemed related to product, none of which necessitated discontinuation of vaccinations, and no serious adverse events attributed to the vaccines. All 6 AEs related to any of the 3 DNAs or placebo were mild and all have resolved. They included 1 lymphadenopathy, 3 alanine aminotransferase increases, 1 aspartate aminotransferase increase, and 1 localized cutaneous erythema. The SAEs or AEs that required expedited reporting to the trial sponsor that were not related to vaccine were appendicitis, severe head injury from a fall, alcohol withdrawal, acute systemic allergic reaction, demyelinating disorder, hepatic mesenchymal hamartoma, and uterine leiomyosarcoma.

**Table 4-6. Summary of local site injection pain and/or tenderness reactogenicity after injections with DNA or placebo in HVTN 106**

Deltoid pain and/or tenderness	Vac 1 N = 105 n (%)	Vac 2 N = 101 n (%)	Vac 3 N = 98 n (%)
None	13 (12%)	17 (17%)	27 (28%)
Mild	68 (65%)	73 (72%)	55 (56%)
Moderate	24 (23%)	11 (11%)	16 (16%)
Severe	0 (0%)	0 (0%)	0 (0%)
Potentially life-threatening	0 (0%)	0 (0%)	0 (0%)

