## 5 Objectives and endpoints

### 5.1 Primary objectives and endpoints Part A

*Primary objective 1:*

To evaluate the safety and tolerability of different doses of CH505TF Env gp120 in HIV-uninfected healthy adults

*Primary endpoint 1:*

Local and systemic reactogenicity signs and symptoms, laboratory measures of safety, and AEs and SAEs

*Primary objective 2:*

To evaluate binding antibody responses elicited by different doses of the CH505TF gp120 vaccine

*Primary endpoint 2:*

HIV-specific binding Ab responses as assessed by binding Ab multiplex assay 2 weeks after the third vaccination with CH505TF gp120

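### Draining lymph nodes are a listed reactogenicity component, but a node check is guaranteed only on day 0, so node reactions on days 1 to 7 are not systematically measured

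*Combined protocol and SAP*

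**What the plan says.** Section 9.10 defines the content of the assessment: "Reactogenicity assessments include assessments of systemic and local symptoms, vaccine-related lesions, and lymph nodes". The period is the day of vaccination and seven full days after it. Section 9.10.3 limits the node part: "This assessment is required only when reactogenicity assessments are performed by HVTN CRS staff, not by the participant". It asks for the nodes draining the injected side, and for a diameter if they are enlarged.

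Table 9-1 sets out who performs each assessment. Two slots belong to site staff alone: "Baseline: before vaccination" and "Early: 25-60 minutes after vaccination". Every later slot, through "Between 12:00am and 11:59pm day 7", may be done by staff or by the participant.

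Section 9.10.1 lists the systemic symptoms and one local symptom, pain or tenderness near the injection site. Neither the groin nor the nodes are mentioned.

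The primary safety endpoint in Section 5.1, repeated in Section 5.4 for Part B, is "Local and systemic reactogenicity signs and symptoms, laboratory measures of safety, and AEs and SAEs". Section 6.4.3.1 tabulates each reactogenicity sign or symptom by arm, counting each participant once at the maximum severity over all injection visits.

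**The concern.** The plan sets a seven-day window for reactions, yet the only node checks it guarantees fall before injection or within an hour after it. A site can follow the protocol exactly and record no node observation on days 1 to 7 for most vaccinations.

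This matters more here than in a standard vaccine trial. Section 4.5.1 places protein and DNA in the same thigh to "ensure that both immunogens reach the same draining lymph nodes", and Section 4.4 says that the adjuvant has not been given to humans with these vaccines. Node reactogenicity is thus a natural safety question for Groups 6 and 8. A table built mainly on checks within an hour of injection could be misread as evidence that there is none.

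**Working it through.** The plan states no figure on this point, so there is none to reproduce. The check is a count of assessment slots and visit days.

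**1. Slots in Table 9-1.** Each vaccination has ten slots: baseline, early, rest of day 0, and days 1 to 7 (3 + 7 = 10). Two are staff-only, both on day 0; eight are staff or participant.
- Part A, five vaccinations: 5 × 7 = 35 slots on days 1 to 7, of which 0 must be done by staff.
- Part B, six vaccinations (Section 8.1, Appendix L): 6 × 7 = 42 slots, of which 0 must be done by staff.

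**2. Scheduled clinic visits on days 1 to 7**, from the day rows of Appendices I to L:

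| Vaccination | Part A: next visit | Part B: next visit |
|---|---|---|
| 1 (D0) | D7, day 7 | D7, day 7 |
| 2 (D56) | D70, day 14 | D70, day 14 |
| 3 (D112) | D126, day 14 | D126, day 14 |
| 4 (D224) | D238, day 14 | D238, day 14 |
| 5 (D364) | D371, day 7 | D378, day 14 |
| 6 (D485) | none | D493, day 8 |

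Appendices K and L print D58 for vaccination 2. The next visit would then be at day 12, still outside the period.

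**3. Coverage.** There are 42 participants in Part A and 90 in Part B (Table 3-1).
- Scheduled vaccinations: 42 × 5 + 90 × 6 = 210 + 540 = 750.
- With a clinic visit on days 1 to 7: Part A 42 × 2 = 84 of 210 (40%); Part B 90 × 1 = 90 of 540 (17%).
- Together: 84 + 90 = 174, and 174/750 = 23.2%.
- If the day-8 visit after vaccination 6 is counted: 174 + 90 = 264, and 264/750 = 35.2%.

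**4. What happens at those visits.** Appendices K and L mark an abbreviated physical examination, which Section 9.4 makes symptom-directed. They mark reactogenicity assessment only at vaccination visits, with a footnote on daily assessment. No text requires nodes to be palpated at the one-week visits.

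**5. Consequence for comparing arms.** Within each part all arms share one visit schedule, so scheduled visits create no imbalance. The other routes do. Under Section 9.10, participants reporting a reaction above mild are in general seen within 48 hours, so an arm with more reported symptoms can get more node checks. Section 6.4.3.1 then takes a maximum over unequal numbers of observations, with no count of how often nodes were examined.

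**The case against.** The strongest reply is that node reactions can reach the data in several other ways. Staff may perform any assessment on days 1 to 7, and the node check is then required. Contact with the site is due within 72 hours, and reactions above mild are in general seen within 48 hours unless improving or resolved. Adverse events are reviewed at every follow-up visit, including about two weeks after each vaccination, and are themselves in the primary endpoint. This stands for clinically evident reactions. It does not restore systematic measurement: the 72-hour contact need not be in person, the 48-hour rule depends on reported symptoms, and none of these routes expressly calls for a node examination.

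The memory tool and case report forms are not in the documents, so a groin item could exist there. The local symptom in Section 9.10.1 might also be stretched to a tender groin. Even so, that would merge it with injection-site pain and would miss painless swelling. Limiting node measurement to staff is a reasonable choice, because palpation needs training, but it is a reason to schedule staff checks.

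A reader might infer four stronger things that the documents do not support:
- **That nodes are a named primary endpoint.** They enter by inference from Sections 5.1, 5.4 and 9.10. Neither the endpoint text nor the combined severity summaries in Section 6.4.3.1 name them.
- **That node reactions will go almost wholly unseen, or that every arm will show close to none whatever the truth.** The routes above rule this out as a statement of fact. A capture percentage would need the share of node reactions still present at day 7, which the plan does not give.
- **That bias will hide reactions most in Groups 6 and 8.** If those groups react more, symptom-triggered visits could give them more node checks. The direction of bias is unknown.
- **That the earlier trial of the DNA product shows a node signal.** Section 4.9.3 reports the related events as "They included 1 lymphadenopathy, 3 alanine aminotransferase increases" and others, but that trial was still blinded, the events are pooled over three DNA products or placebo, and all were mild and resolved.

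**Conclusion.** The point holds in a limited form. Node checks are guaranteed only before injection and within an hour after it. None of the 35 (Part A) or 42 (Part B) daily slots on days 1 to 7 must be done by staff, and 23% of scheduled vaccinations have a clinic visit in that period. Day 1 to 7 node data will therefore be opportunistic. Mild or asymptomatic reactions are likely to be under-ascertained, and comparison between arms is unreliable because detection depends on other symptoms.

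The slot count rests on the text alone. The 23% rests on nominal visit days and full attendance. Visit windows are in the Study Specific Procedures, which are not in the documents; if every sixth-vaccination follow-up in Part B fell within seven days, the figure would be 35%. This is a worthwhile, inexpensive improvement and does not threaten the safety objective as a whole.

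**What to change.** - In Section 9.10.1 and on the memory tool, add a participant-recorded item for swelling or tenderness in the groin on the injected side, for days 0 to 7 after every vaccination.
- In Section 9.10.3, require the staff node check at the one-week visits already scheduled: D7 in both parts, D371 in Part A and D493 in Part B. Compare each finding with the check before that vaccination. This gives a required check at about one week for 264 of 750 vaccinations (35%); the self-report item covers the rest.
- In Section 6.4.3.1, tabulate node findings by arm and time with the number examined at each, and keep day-0 checks separate from later ones.

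The cost is one line on the memory tool and case report form, and brief palpation at visits that already include an abbreviated examination. A few incidental palpable nodes will be recorded; the check before vaccination helps to identify them. If the sponsor prefers no new procedure, the protocol should at least say that day 1 to 7 node data are opportunistic and report them with the numbers examined.
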